5.5.1.5 Any toxicity requiring interruption of study drug during a cycle of therapy

THIS PROTOCOL IS FOR RESEARCH PURPOSES ONLY, SEE PAGE 1 FOR USAGE POLICY
for ≥ 7 days or which recurs upon drug challenge.

5.5.1.6 Note: Allergic reactions that necessitate discontinuation of study drug will not be considered a dose-limiting toxicity.

5.5.2 Hematological dose limiting toxicity

5.5.2.1 Hematological dose limiting toxicity is defined as:

- In patients evaluable for hematological toxicity (see [Section 4.1.8.1](#)), Grade 4 thrombocytopenia (platelet count $< 25,000/\text{mm}^3$) or Grade 4 neutropenia (see [Section 6.1](#)), not due to malignant infiltration.
- Myelosuppression that causes a delay of > 14 days between treatment cycles.
- In patients with CNS tumors, requirement of platelet transfusion(s) for platelets $\leq 50,000/\text{mm}^3$ on more than one occasion during a cycle will be considered a DLT. *I.e.* If a patient with a CNS tumor requires more than one platelet transfusion to achieve a count $> 50,000/\text{mm}^3$ (poor initial response, etc.) on one occasion this is not a DLT, but if it occurs again during the cycle, it will be dose limiting.

6.0 DOSE MODIFICATIONS FOR ADVERSE EVENTS

The Study Chair must be notified of any dosage modification or use of myeloid growth factor. If a patient's dose is reduced due to toxicity, any future XL184 total weekly dose should not exceed a previously un-tolerated dose.

6.1 Dose Modifications for Hematological Toxicity

- 6.1.1 If a patient experiences dose-limiting Grade 4 neutropenia or thrombocytopenia, the treatment will be withheld. Counts should be checked every 3 - 4 days for thrombocytopenia and every other day for neutropenia during this time. If the toxicity resolves to meet eligibility parameters within 14 days of drug discontinuation, the patient may resume treatment at the next lower dose level (See [Appendix IIB](#)). Doses reduced for toxicity will not be re-escalated, even if there is minimal or no toxicity with the reduced dose.
- 6.1.2 If dose-limiting toxicity does not resolve to meet eligibility or baseline parameters within 14 days of drug discontinuation, the patient must be removed from protocol therapy.
- 6.1.3 Two dose reductions will be allowed for toxicity. If a patient experiences a dose-limiting toxicity after two dose reductions, they must be removed from protocol therapy.

6.2 Dose Modifications for Non-Hematological Toxicity

- 6.2.1 If a patient experiences non-hematological dose-limiting toxicity as defined in [Section 5.5.1](#), the treatment will be withheld. If the toxicity resolves to meet eligibility or baseline parameters within 14 days of drug discontinuation, the patient may resume treatment at the next lower dose level (See [Appendix IIB](#)). Doses reduced for toxicity will not be re-escalated, even if there is minimal or no toxicity with the reduced dose.
- 6.2.2 If dose-limiting toxicity does not resolve to meet eligibility or baseline parameters within 14 days of drug discontinuation, the patient must be removed from protocol therapy.
 - 6.2.2.1 The exception to this is Grade 3 weight loss as it is unlikely that the patient would return to baseline within 14 days. Patients who experience Grade 3 weight loss may resume study medication after 14 days with a dose-reduction (see [Appendix II-B](#)) if the patient is deriving benefit from therapy, the weight loss has stabilized and the treating physician feels it is in the best interest of the patient. Patients should be removed from protocol therapy if their weight loss is $\geq 20\%$ from baseline and persists for ≥ 28 days after the introduction of supplemental NG/G tube feeding or TPN.
- 6.2.3 Two dose reductions will be allowed for toxicity. If a patient experiences a dose-limiting toxicity after two dose reductions, they must be removed from protocol therapy.

[figure not shown]

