4.1 Inclusion Criteria

4.1.1 Age: Patients must be ≥ 2 and ≤ 18 years of age at the time of study enrollment.

4.1.2 Body Surface Area (BSA): Patients must have a body surface area $\geq 0.44 \text{ m}^2$ when enrolling on dose level -1. Patients must have a body surface area $\geq 0.35 \text{ m}^2$ when enrolling on dose levels 1, 2, or 3.

4.1.3 Diagnosis:

Part A: Patients with relapsed or refractory solid tumors (excluding medullary thyroid cancer) including CNS tumors and malignant melanoma are eligible. Patients must have had histologic verification of malignancy at original diagnosis or relapse except in patients with intrinsic brain stem tumors, optic pathway gliomas, or patients with pineal tumors and elevations of CSF or serum tumor markers including alpha-fetoprotein or beta-HCG.

Part B: Patients with medullary thyroid cancer (MTC), with or without bone marrow involvement, will be eligible for Part B. These patients will be enrolled at Dose Level 2, the recommended Phase 2 Dose determined in the dose escalation part of the study.

4.1.4 **Disease Status:**
Patients must have either measurable or evaluable disease (see Sections [12.2](#) and [12.3](#) for definitions).

4.1.5 **Therapeutic Options:** Patient's current disease state must be one for which there is no known curative therapy or therapy proven to prolong survival with an acceptable quality of life.

4.1.6 **Performance Level:** Karnofsky $\geq 50\%$ for patients > 16 years of age and Lansky ≥ 50 for patients ≤ 16 years of age (See [Appendix I](#)). Note: Neurologic deficits in patients with CNS tumors must have been relatively stable for at least 7 days prior to study enrollment. Patients who are unable to walk because of paralysis, but who are up in a wheelchair, will be considered ambulatory for the purpose of assessing the performance score.

4.1.7 **Prior Therapy**

4.1.7.1 Patients must have fully recovered from the acute toxic effects of all prior anti-cancer chemotherapy.

- a. **Myelosuppressive chemotherapy:**
At least 21 days after the last dose of myelosuppressive chemotherapy (42 days if prior nitrosourea).

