5.3 Dose Escalation Schema

5.3.1 *Inter-Patient Escalation- (Part A) COMPLETE*

The starting dose will be 30 mg/m² (Dose Level 1) with dose levels for subsequent groups of patients as follows.

Dose Level	XL184 Dose (mg/m² po daily)
-1	23
1*	30
2	40
3	55

** Starting Dose Level*

There will be no escalations beyond dose level 3 (55 mg/m²).

If the MTD has been exceeded at the first dose level, then the subsequent cohort of patients will be treated at a dose of 23 mg/m² (Dose Level -1).

With Amendment #5A, patients enrolled onto Part A of the study will be treated at the recommended Phase 2 dose, which has been determined to be Dose Level 2 (40 mg/m²).

5.3.2 *Part B: Patients with medullary thyroid cancer (MTC) can be accrued to a separate stratum if there are no available slots on Part A. These patients will be enrolled at one dose level below the dose level at which patients on Part A are actively enrolling, or at the starting dose level (Dose Level 1) if dose escalation has not yet occurred. COMPLETE*

With Amendment #5A, patients enrolled onto Part B of the study will be treated at the recommended Phase 2 dose, which has been determined to be Dose Level 2 (40 mg/m²).

5.3.3 *Intra-Patient Escalation (Patients with MTC only)*

Intra-patient dose escalation will be allowed for patients with MTC remaining on study in cycles of therapy subsequent to Cycle 1, once an MTD or recommended Phase 2 dose is identified, if the patient has not experienced dose-limiting toxicity at the dose at which they began therapy. Patients who are one dose level below the MTD can escalate to the MTD. Patients who are more than one dose level below the MTD can escalate one dose level per cycle until they reach the MTD as long as they do not experience a DLT when escalating. Sites have to confirm with the Study Chair and the COG Phase 1 Operations office that their patient may proceed with an intra-patient dose escalation following the completion of Cycle 1 or subsequent cycles. COMPLETE

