APPENDIX IIA: XL184 DOSING NOMOGRAM

Patients must have a body surface area $\geq 1.04 \text{ m}^2$ when enrolling on dose level -1, a BSA $\geq 0.96 \text{ m}^2$ to enroll on dose level 1, a BSA $\geq 0.72 \text{ m}^2$ to enroll on dose level 2, and a BSA $\geq 0.65 \text{ m}^2$ to enroll on dose level 3. If dose reduction is required due to toxicity, patients will decrease their administered dose per the tables below each respective dose level.

Patients enrolled after Amendment #1 should follow the dosing nomogram in [Appendix IIB](#). Patients enrolled on study **prior to Amendment #1** must not change their dosing schedule and should continue to use the same dosing nomogram below.

Dose Level -1

Dose Level 23 mg/m² (DOSE LEVEL -1)

BSA (m ²)	Dose (mg)	Total Weekly Dose (mg)
1.04 – 1.55	40 mg po q M, W, Th, Sat, Sun	200 mg
1.56- \geq 2.00	40 mg once daily	280 mg

Dosing if Dose Reduction for Toxicity at 23 mg/m² Dose Level

BSA (m ²)	Dose (mg)	Total Weekly Dose
1.04 – 1.55	20 mg once daily	140 mg
1.56 - \geq 2.00	40 mg po q M, W, Th, Sat, Sun	200 mg

Dose Level 1

XL184 Dose Assignment: 30 mg/m² (DOSE LEVEL 1)

BSA (m ²)	Administered dose (mg)	Total Weekly Dose (mg)
0.96 – 1.14	40 mg po q M, T, W, Fri, Sat, Sun	240 mg
1.15 – 1.42	40 mg po once daily	280 mg
1.43 – 1.67	60 mg po q M, T, W, Fri, Sat, Sun	360 mg
1.68 – \geq 2.0	60 mg po once daily	420 mg

Dosing if Dose Reduction for Toxicity at 30 mg/m² Dose Level

BSA (m ²)	Administered dose (mg)	Total Weekly Dose (mg)
0.96 – 1.14	60 mg po q M, W, Fri	180 mg
1.15 – 1.42	40 mg po q M, W, Th, Sat, Sun	200 mg
1.43 – 1.67	40 mg po once daily	280 mg
1.68 – \geq 2.0	60 mg po q M, W, Th, Sat, Sun	300 mg

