BSA (m²)	BSA (m²)	BSA (m²)	BSA (m²)	Weekly Dose/ Schedule for Initial Dosing	Weekly Dose/Schedule for 1st Dose Reduction due to Toxicity	Weekly Dose/Schedule for 2nd Dose Reduction due to Toxicity
		1.86 – 2.07	1.36 – 1.5	560 mg = 80 mg Daily	420 mg = 60 mg Daily	300 mg = 60 mg M, W, Th, Sat, Sun
		≥ 2.08	1.51 – 1.68	600 mg = 100 mg M, T, W, F, Sat, Sun	420 mg = 60 mg Daily	300 mg = 60 mg M, W, Th, Sat, Sun
			1.69 – 2.00	700 mg = 100 mg Daily	480 mg = 80 mg M, T, W, F, Sat, Sun	360 mg = 60 mg M, T, W, F, Sat, Sun
			≥ 2.01	840 mg = 120 mg Daily	600 mg = 100 mg M, T, W, F, Sat, Sun	420 mg = 60 mg Daily

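### The dose-reduction text of Sections 6.1 and 6.2 and the reduction columns of Appendices IIA and IIB do not always give the same resumed dose or the same number of allowed reductions

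*Combined protocol and SAP*

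**What the plan says.** Section 6.2.1 (non-hematological toxicity) provides that, once a DLT has resolved within 14 days, "the patient may resume treatment at the next lower dose level", followed by a pointer to Appendix IIB. Section 6.1.1 uses the same words for hematological toxicity. Section 6.2.3, like 6.1.3, adds: "Two dose reductions will be allowed for toxicity". It continues: "If a patient experiences a dose-limiting toxicity after two dose reductions, they must be removed from protocol therapy".

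Section 5.3.1 defines the dose levels: "The starting dose will be 30 mg/m² (Dose Level 1) with dose levels for subsequent groups of patients as follows". The table there lists -1, 1, 2 and 3 at 23, 30, 40 and 55 mg/m². Since Amendment #5A, both parts enroll at Dose Level 2 (40 mg/m²).

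Appendix IIB gives a BSA column for each of the four levels. It also has a column headed "Weekly Dose/Schedule for 1st Dose Reduction due to Toxicity" and a matching one for the second reduction, both keyed to the row of the initial weekly dose. In the two lowest rows (80 and 100 mg/week) the second-reduction cell takes the patient off therapy.

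Patients enrolled before Amendment #1 stay on Appendix IIA, under which "patients will decrease their administered dose per the tables below each respective dose level". Each level tabulated there has a single reduction table.

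**The concern.** The resumption rule uses a defined term and then points to a table that can be read in two ways. One reader moves one defined level down and reads that level's column at the child's BSA. Another reads the labelled first-reduction column. If the two gave the same dose, the wording would not matter, but often they do not.

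The number of reductions is also not settled. The text gives two with no exception; some rows of Appendix IIB and the tables of Appendix IIA give one. One passage can therefore keep a child on therapy where another removes the child.

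At stake are the dose after a DLT, the description of later-cycle toxicity (a primary aim under Section 1.1.2) and time on therapy. The rule is used in practice: Section 2.6 reports later-cycle DLTs in 10 of 29 patients as of January 2014. Sections 6.3, 6.4, 6.6, 6.7 and 7.8 send other toxicities through Section 6.1.1 or Section 6.2, so the same wording governs those too.

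**Working it through.** The plan states no figure for this point, so there is nothing to reproduce. The check compares Appendix IIB with itself.

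**Inputs.** Dose levels are from Section 5.3.1; weekly doses, BSA bands and reduction columns are from Appendix IIB. The BSA distribution of patients is not given. Assumption: a uniform grid in steps of 0.01 m² from 0.50 to 2.01 m², which is 152 values.

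**Comparison.** For each BSA, ratio = (first-reduction weekly dose in the Dose Level 2 row) / (initial weekly dose in the Dose Level 1 column at the same BSA). A ratio other than 1 is a discrepancy.

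| BSA (m²) | Initial dose at 40 mg/m² (mg/week) | First-reduction column | Dose Level 1 column | Ratio | Grid values |
|---|---|---|---|---|---|
| 0.53–0.55 | 140 | 100 | 120 | 0.83 | 3 |
| 0.61–0.64 | 160 | 120 | 140 | 0.86 | 4 |
| 0.74–0.78 | 200 | 140 | 160 | 0.88 | 5 |
| 0.86–0.90 | 240 | 160 | 200 | 0.80 | 5 |
| 1.05–1.09 | 280 | 200 | 240 | 0.83 | 5 |
| 1.10–1.17 | 300 | 200 | 240 | 0.83 | 8 |
| 1.22–1.36 | 360 | 240 | 280 | 0.86 | 15 |
| 1.37–1.46 | 420 | 300 | 280 | 1.07 | 10 |
| 1.58–1.65 | 420 | 300 | 360 | 0.83 | 8 |

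Total: 3+4+5+5+5+8+15+10+8 = 63, and 63/152 = 41.4%. The reduction column is lower at 53 values (34.9%) and higher at 10 (6.6%). At BSA 1.12–1.17 its 200 mg/week equals the Dose Level -1 dose, two defined levels down.

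**Sensitivity to the grid.** From 0.35 (the Dose Level 2 minimum in Section 4.1.2) to 2.07 m²: 71/173 = 41.0%. From 0.44 to 2.20: 71/177 = 40.1%. From 0.35 to 2.00: 71/166 = 42.8%. From 0.35 to 2.50: 107/216 = 49.5%. Starting at 0.35 adds the band 0.35–0.39, with 60 v 80 mg/week (ratio 0.75).

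**Other steps, grid 0.50–2.01.** First reduction from Dose Level 1 against Dose Level -1: 86/152 = 56.6%. First reduction from Dose Level 3 against Dose Level 2: 51/152 = 33.6%. Second reduction from Dose Level 2 against Dose Level -1: 126/152 = 82.9%.

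**Number of reductions, passages side by side.**
- Sections 6.1.3 and 6.2.3: two, with no exception by BSA or enrollment date.
- Appendix IIB, 80 and 100 mg/week rows: one, then off therapy. These rows cover BSA 0.35–0.52 at Dose Level 1 and 0.35–0.39 at Dose Level 2. They also cover 0.44–0.68 at Dose Level -1, where Section 2.6 shows no enrollment as of January 2014 (6+11+12 = 29 at Levels 1 to 3).
- Section 5.3.1: one defined level lies below Dose Level 1. A patient who started there cannot take two reductions by moving down defined levels.
- Appendix IIA: one reduction table per tabulated level, while Sections 6.1.1 and 6.2.1 cite Appendix IIB alone.

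**The case against.** The strongest reply is that the sentence does not stop at the dose level. It sends the reader to Appendix IIB, which has columns labelled for first and second reductions for toxicity. Sections 6.2.2.1 and 6.8 also send reductions to that appendix. Moving down defined levels cannot work as a general rule, since nothing lies below Dose Level -1 and only one level lies below Dose Level 1, yet the appendix prints reductions for both. This largely stands: the reduction columns are the more natural reading. It does not settle the matter, because the dose-level columns are in the same appendix and Section 5.3.3 uses the same term for moves between defined levels.

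On the number of reductions, two can be read as a ceiling, which would fit the rows that end after one. The text does not say so, and it ties removal to a DLT after two reductions. At the current dose the conflict covers only BSA 0.35–0.39, likely rare from age 2; the Appendix IIA conflict concerns only patients enrolled before Amendment #1, whose number is not given.

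Further safeguards exist. Section 6.0 requires that the Study Chair be told of any dose modification, so divergent readings may be caught centrally, although that is not a written dosing rule. The patient diary (Appendix III) already records the weekly dose per nomogram and the tablets prescribed and taken each day.

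A reader might infer that about 41% of children are dosed wrongly after a DLT. The documents do not support that: the figure is a share of evenly spaced BSA values, it applies only if a site uses the dose-level columns, and no site is shown to have done so. A reader might also infer a threat to the MTD, the recommended dose or cohort closure. Sections 11.1 and 11.2.2 base the MTD and closure rules on Cycle 1 DLTs, and a dose resumed after a DLT does not change whether that DLT counted. Nor can a material change in exposure be assumed: Section 2.6 reports mean steady-state AUC of 31.9, 33.3 and 33.7 µg·h/mL at 30, 40 and 55 mg/m², with six patients each.

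**Conclusion.** The inconsistency is real and limited in reach. Two parts should be kept apart.

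- **Resumed dose.** A defined term conflicts with the table it cites. For the first reduction from Dose Level 2 the two readings differ at about 41% of BSA values on the 0.50–2.01 m² grid, with ratios from 0.80 to 1.07. This rests on the uniform grid and on a site taking the less natural reading. The figures for Dose Levels 1 and 3 matter only for patients who started there and remain on therapy.
- **Number of reductions.** The general allowance of two does not match the two lowest rows of Appendix IIB or the tables of Appendix IIA. These mismatches do not depend on which column a site reads for the first reduction. They are narrow at 40 mg/m².

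What can depend on the reading is the post-DLT dose, the later-cycle toxicity description and time on therapy. Which dose or removal rule is right is not a question this review answers; the passages must be reconciled.

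**What to change.** Reconcile Sections 6.1.1, 6.1.3, 6.2.1 and 6.2.3 with Appendices IIA and IIB so that every patient has one resumed dose and one number of allowed reductions. The text should say whether the resumed dose is read from the reduction columns or from the next defined level's column, with the text or the table changed to match. The allowance of two reductions should be made to agree with the rows that end after one and with Appendix IIA, and the resumption rule should name the appendix that applies to patients enrolled before Amendment #1. The sponsor decides which passage governs.

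The cost is a wording amendment. No new data collection is needed, because the diary already captures doses prescribed and taken.

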6.3 Dose Modifications for Proteinuria

THIS PROTOCOL IS FOR RESEARCH PURPOSES ONLY, SEE PAGE 1 FOR USAGE POLICY

- If urinalysis shows \geq trace protein then obtain UPC.
- If the urine protein/creatinine (P/C) ratio ≤ 1.9 continue XL184. If patient has Grade 3 proteinuria (urine protein/creatinine (P/C) ratio > 1.9), a second measurement should be obtained within 72 hours. A second confirmation of Grade 3 proteinuria will be considered a DLT.
- If the second measurement confirms Grade 3 proteinuria (urine protein/creatinine (P/C) ratio > 1.9), then interrupt XL184 treatment and reassess weekly.
- If XL184 is held for ≥ 14 days then remove from protocol therapy. If the urine protein/creatinine (P/C) ratio decreases to ≤ 1.9 in < 14 days then resume XL184 at a lower dose as outlined in [Section 6.2.1](#).
- Monitor the UPC weekly for 2 consecutive weeks once protocol therapy resumes.

6.4 Dose Modifications for Hypertension

- **Baseline blood pressure (BP)** is defined as the blood pressure obtained at the examination used for study enrollment. This baseline BP should be obtained as follows: 1) Obtain 3 serial blood pressures from the same extremity with the patient in the same position at rest with an appropriately sized cuff that are separated by at least 5 minutes. Avoid using the lower extremity if possible. 2) Average the systolic blood pressure from the 2nd and 3rd measurements. 3) Average the diastolic blood pressure from the 2nd and 3rd measurements. 4) The baseline BP is the average of the systolic over the average of the diastolic measurements.
- **Elevation** in either the systolic or diastolic blood pressure should be considered when following the algorithm below.
- **The upper limit of normal (ULN)** is defined as a BP equal to the 95th percentile for age, height, and gender. See [Appendix VIII](#).
- The NCI CTCAE will be utilized to determine the grade of hypertension for reporting purposes.
- Elevated BP measurements should be repeated on the same day to confirm the elevation. If confirmed, patients with elevated BP should have BP measurements performed at least twice weekly until BP is \leq ULN.
- The algorithm below will be used to manage XL184- related hypertension.
- Hypertension should be managed with appropriate anti-hypertensive agent(s) as clinically indicated. It is strongly recommended that nephrology or cardiology be consulted in the evaluation and management of hypertension.

Elevations in BP are based on systolic or diastolic pressures.

[†] Elevated blood pressure (BP) measurements should be repeated on the same day to confirm the elevation. Patients with elevated BP at any time should have BP measurements performed at least twice weekly until BP is within the ULN.

[§] ULN (Upper Limit of Normal) is a BP equal to the 95th percentile from age, height, and gender-appropriate normal values (Appendix VIII).

^{*} If BP >25 mm Hg above ULN for age (verified) or Grade 4 HTN at any time, hold drug. Study drug should also be held for BP ≤ 25 mm Hg above the ULN age for > 14 days or 35 mmHg above baseline for > 14 days. Antihypertensive agents can be used to control hypertension as clinically indicated after study drug is held.

[^] Anti-hypertensive therapy should be prescribed as clinically indicated, including the use of multiple anti-hypertensive agents.

[#] Baseline BP is defined in Section 6.4.

Arm 1 of algorithm:

- If blood pressure (BP) ≤ 95% for age, height, and gender, continue XL184 at the same dose.

Arm 2 of algorithm:

- If BP ≤ 10 mm Hg above the ULN for age, height, and gender, continue XL184 at the same dose and recheck the BP within 72 hours.
 - If the BP is ≤ ULN on recheck, continue XL184 at the same dose.
 - If the BP remains above the ULN on recheck, then start antihypertensive therapy ([Section 7.7](#)) and follow Arm 3 of the algorithm from the point that anti-hypertensive therapy is started.

Arm 3 of algorithm:

- If BP is 11 to 25 mm Hg above the 95% for age, height, and gender on ≥ 2 of 3 measurements or > 35 mmHg above baseline on ≥ 2 of 3 measurements, start antihypertensive therapy (see [Section 7.7](#)), continue XL184 at the same dose, and monitor BP at least twice weekly.
 - If the BP returns to ≤ ULN within 14 days, continue XL184 at the same dose and continue anti-hypertensive therapy.

THIS PROTOCOL IS FOR RESEARCH PURPOSES ONLY, SEE PAGE 1 FOR USAGE POLICY

- If the BP remains elevated \leq 25 mm Hg above the 95% or $>$ 35 mm Hg above baseline for more than 14 days after the institution of anti-hypertensive therapy, **hold** XL184, monitor BP at least every 3 days, and follow Arm 4 of the algorithm from the point that XL184 is held. The antihypertensive therapy should be continued until the BP is less than the ULN.
 - If the BP returns to \leq ULN within 14 days, restart XL184 at a reduced dose ([Section 6.1.1](#)).
 - If the BP remains $>$ ULN for more than 14 days, patient is Off Protocol Therapy.
- If the BP increases to $>$ 25 mm Hg above the ULN despite anti-hypertensive therapy, **hold** XL184, but continue the anti-hypertensive agent(s). Monitor the BP as clinically indicated and follow Arm 4 of the algorithm from the point that XL184 is held.
 - If the BP is \leq ULN within 14 days, XL184 may be restarted at a reduced dose ([Section 6.2.2](#)).
 - If the BP is $>$ ULN for $>$ 14 days, the patient is Off Protocol Therapy ([Section 10.1](#)).

Arm 4 of algorithm:

- If BP is $>$ 25 mm Hg above the 95% for age, height, and gender **hold** XL184, monitor BP and administer anti-hypertensive therapy as clinically indicated.
 - If the BP returns to \leq ULN within 14 days, XL184 may be restarted at a reduced dose ([Section 6.2.2](#)).
 - If the BP is $>$ ULN for $>$ 14 days, the patient is Off Protocol Therapy ([Section 10.1](#)).

Arm 5 of algorithm:

- If the participant develops Grade 4 hypertension, **discontinue** XL184, monitor BP and administer anti-hypertensive therapy as clinically indicated. The patient is Off Protocol Therapy ([Section 10.1](#)).

6.5**Dose Modifications for DVT**

If a patient develops a DVT while on study, XL184 should be held until adequate anticoagulation is established. Full dose anticoagulation with warfarin is not permitted. Heparins should be used for anticoagulation. The drug may be resumed with a dose reduction if the DVT is dose-limiting (i.e. \geq grade 3) and if the patient is deriving clinical benefit.

6.6**Dose Modifications for Liver Toxicity**

XL184 should be held for grade 3 elevation of ALT, AST or bilirubin. Note: For the purposes of this trial the ULN for ALT is defined as 45 U/L. XL184 may be re-administered at the same dose if levels of ALT, AST and bilirubin meet eligibility criteria or baseline within 7 days of drug discontinuation. Elevated laboratory parameters should be checked at least twice weekly until eligibility criteria is met.

If lab values do not resolve to initial eligibility criteria or baseline within 7 days of interruption or if toxicity recurs with re-challenge, then this will be considered dose-limiting per [section 5.5.1](#). XL184 will then be dose-reduced according to [Section 6.2.1](#) when eligibility criteria is met.

